5.2 Analytic Design

COTA, a data and analytic company headquartered in Boston MA, was founded by physicians at the John Theurer Cancer Center at Hackensack University Medical Center (an HMH site) in 2011. The company is experienced in the handling of large observational databases. Current shareholders of COTA include Hackensack Meridian Health and some of its physicians. COTA currently has a business associate agreement with Hackensack University Medical Center and several additional HMH sites which would permit abstraction of PHI if required. COTA will only receive de-identified data to perform secondary research analysis.

Governmental agency (including but not limited to the CDC and FDA) have been contacted about this observational database and will be given access to data as requested.

5.3 Registry Population

5.31 Registry Population Inclusion Criteria

5.311 Confirmed or suspected COVID-19

5.312 Data available via the EPIC system

5.313 NO age restriction

5.314 NO pregnancy restrictions

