4.1 Primary Objectives

- 4.11 Understand epidemiology including presenting features of the COVID-19 pandemic within the Hackensack Meridian Network
- 4.12 Explore the impact of co-morbidities and other patient factors on the severity of COVID-19
- 4.13 Understand need for hospitalization, ICU support and other healthcare resources among patients with COVID-19
- 4.14 Explore efficacy and toxicity of various treatment strategies including “off-label use” of medications in real world settings
- 4.15 Measure clinical outcomes including hospital discharges and survival

5 Research Methods

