5.1 Registry Design and Collection

The Hackensack Meridian Health RWD Observational COVID-19, a descriptive observational database, is a multi-center initiative collecting data throughout the Hackensack Meridian Health Network (HMH).

The database will be drawn from the electronic health records of patients with confirmed or suspected COVID-19. HMH utilizes the EPIC system at most of the facilities, which will serve as the primary data source. Additional data obtained via other HMH staff and

bioinformatics can be added to the database as available and permitted. This includes but is not limited to data obtained either directly from EPIC or provided by other sources such as the HMH Business Intelligence Office (BI) to facilitate data extraction. Reports provided by BI can be entered directly into the REDCap database or kept separately (as pre-data supplements that might be added at a later time).

The database will be designed within the REDCap system. REDCap is a secure web application for building and managing online surveys and databases. While REDCap can be used to collect virtually any type of data (including 21 CFR Part 11, FISMA, and HIPAA-compliant environments), it is specifically geared to support online or offline data capture for research studies and operations.

The REDCap hosted universal observational database can export HIPAA compliant files for external analysis as part of the secondary research usage clause defined by the OHRP.

Data collection fields enumerating the common prognostic variables, treatment regimens and clinical outcomes have been designed by the principal investigator and the study team with input from the Centers of Disease Control and Prevention (CDC).

The abstraction process into the database will be performed by members of HMH who are approved to have access to the EPIC system or provided by BI. Outside abstraction, which would involve viewing of PHI, will not be permitted unless specifically granted by the IRB.

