5.4 Site Responsibilities

5.41 HMH abstract of data from the EPIC system.

5.42 All eligible patients with COVID-19 will be included.

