6.1 Informed Consent

The Principal Investigator believes that the elements for a full waiver of consent under 45 C.F.R. §46.116 are met. Specifically, in order to waive consent the following requirements must be met:

- (1) The research involves no more than minimal risk to the subjects;
- (2) The waiver or alteration will not adversely affect the rights and welfare of the subjects;
- (3) The research could not practicably be carried out without the waiver or alteration; as COVID-19 populations have received treatment and have been discharged or deceased.

The study protocol represents an observational review of patients with confirmed or suspected COVID-19. No interventions are required for enrollment of patients into this database. There will be no direct contact any patient. Protected health information (PHI) will not be made available (pursuant to the HIPAA Privacy Rule as described below) and only aggregate data will be disclosed. The data collection will be conducted across HMH network drawing information from a variety of healthcare settings, with data drawn principally from the electronic health records utilized by the network. It would not be practical (item 3) by the Investigators to obtain consent across the network (which includes multiple hospitals and clinics across the state) as no contact will occur between the study team and the potential subjects. This is an observational study. The subjects will be receiving standard of care therapy at multiple sites, with their consent for the care per usual practice, and will not be made aware of the collection of the data nor will their treating physicians as to keep the therapy unbiased by participation in this study.

Furthermore, this study will involve only collection of data that has or will be obtained for care of the patient/subject. Thus the study may be considered “secondary research” under the revised common rule that became effective January 2020. Unlike the pre-2018 rule exemption for secondary use of information and biospecimens, the Final Rule has no requirement that the information and biospecimens must be pre-existing at the time that the investigator begins the research; prospective collection is permitted.

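### Does requiring EPIC data for entry leave the network-level objectives without a stated scope?

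*Combined protocol and SAP*

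**What the plan says.** Section 5.31 sets the entry conditions: confirmed or suspected COVID-19, then "5.312 Data available via the EPIC system", with no restriction on age or pregnancy. Section 5.42 adds "All eligible patients with COVID-19 will be included", so completeness is promised only for those who meet 5.31. Sections 5.41 and 6.2 also name EPIC as the source. On coverage, section 5.1 states: "HMH utilizes the EPIC system at most of the facilities, which will serve as the primary data source".

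The wider language sits elsewhere. Objective 4.11 is "Understand epidemiology including presenting features of the COVID-19 pandemic within the Hackensack Meridian Network". Section 5.1 and the synopsis say that data come from throughout the network. Section 6.1 says "The data collection will be conducted across HMH network drawing information from a variety of healthcare settings". Table 1-1 gives the network as the participating centers. Objectives 4.13, "Understand need for hospitalization, ICU support and other healthcare resources among patients with COVID-19", and 4.15, "Measure clinical outcomes including hospital discharges and survival", name neither the network nor EPIC.

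Sections 5.1 and 5.6 also allow data from the HMH Business Intelligence Office (BI) and other HMH sources. Neither says whether a patient with no EPIC record can enter by that route.

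**The concern.** If EPIC is at most facilities, some facilities lack it. Patients seen only there would fail 5.312 and never enter, and whether a patient enters would then depend partly on where care was given. Facilities on a different record system need not resemble the rest in case mix, resource use or mortality. In a descriptive registry the population described is a large part of the result, so a mortality or ICU figure labelled as the network's could in truth belong to a subset of it.

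The registry's own variables would not reveal this. Site of care and cases per hospital show which hospitals contribute, but not which are absent. The caution in 5.7 (Quality Control) is generic and says nothing about coverage.

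**Working it through.** The plan states no sample size, precision target or network-level estimate, so there is no figure to reproduce. The check is a comparison of passages, followed by the size a gap could have.

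**1. Is the population defined?** Yes. The section headed Registry Population carries the EPIC condition, and 5.42 refers back to it through the word eligible. Objectives are read through the inclusion criteria, and they do not normally restate them.

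**2. Do the passages contradict one another?**

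| Place | What it says about scope | In conflict with 5.312? |
|---|---|---|
| 4.11 | pandemic within the network | Loosely: silent on EPIC, but does not claim every facility or case |
| 4.13, 4.15 | no site scope at all | No |
| Synopsis, 5.1, 6.1 | throughout or across the network | No: describes a multi-center setting |
| Table 1-1 | network as participating centers | No: a list of responsible parties |
| 5.1 | EPIC at most facilities | No: this discloses the limit |

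One phrase in one objective is left.

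**3. Is anyone shown to be excluded?** Exclusion needs a COVID-19 patient treated at a non-EPIC facility who has no EPIC data from anywhere in HMH. The word facilities is not defined. Nothing says that those without EPIC treat COVID-19 patients, and such a patient may hold an EPIC record from another HMH site. Selection by site of care is a possibility only.

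**4. How large could the gap be?** Let s be the share of network cases without EPIC data, r the proportion with an outcome among patients with EPIC data, and q the proportion among those without.

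- Network value = (1 − s)r + sq
- EPIC value minus network value = r − (1 − s)r − sq = s(r − q)

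The documents give none of s, r or q. The word most bounds the share of facilities without EPIC (above 0%, below 50%) but does not bound the share of cases. On assumed inputs:

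- s = 0: difference 0, whatever r and q are
- s = 5%, |r − q| = 5 points: 0.05 × 5 = 0.25 points
- s = 20%, |r − q| = 15 points: 0.20 × 15 = 3.0 points

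If q may take any value from 0 to 1, the network proportion lies between (1 − s)r and (1 − s)r + s, a band of width s. With r = 20% and s = 10%, both assumed, that is 0.9 × 20% = 18% up to 18% + 10% = 28%. The ends require that none, or all, of the uncovered patients have the outcome. The band shows the effect of knowing nothing about q and is not evidence of bias in this registry.

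**5. What would a change alter?** A scope sentence in the objectives leaves the cohort, the analyses in 5.71 and every estimate as they are: r is reported either way. Widening 5.312 would alter the cohort, but only if BI or another source holds the key 5.6 variables for patients without EPIC data, which the documents do not show. It would also bring in records likely to be less complete, because the registry relies on reading the full record (5.53, 5.7).

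**The case for a change.** The best case for a change is that it is cheap and that readers of the output may not have section 5.3 in front of them. Results may be published (7.1) and released to governmental agencies (7.2), and a figure from a network registry is easily taken as network-wide. The remark about most facilities is made in passing, as a point about data source, and is not carried into the objectives or the limitations. One sentence and a count of uncovered facilities would settle the matter without new patient-level data.

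Part of this stands. The phrase in 4.11 is looser than the criterion, and a report should describe its population as patients with confirmed or suspected COVID-19 and data in EPIC, naming uncovered facilities where known. But that is ordinary reporting: any competent methods section states the inclusion criteria and the data source. Counting uncovered cases, as opposed to facilities, would need data from outside the registry.

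The role of BI is a separate ambiguity. Section 5.1 lets BI reports go straight into the database but describes them as additional data and as an aid to extraction. On that reading EPIC defines the cohort and BI supplements it. If BI can in fact supply whole patients, 5.312 is merely out of date, and narrowing the objectives would be the wrong remedy. The text does not settle which holds, and that is a further reason not to rewrite the objectives on an assumption.

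**Conclusion.** No change is needed. The entry condition and the incomplete EPIC coverage are both on the page, in the sections where a reader would look for them. The mismatch is confined to the wording of 4.11; 4.13 and 4.15 make no claim about the network. The effect on results is unknown and may be nil. The 0.25 to 3.0 point range rests wholly on assumed shares and differences, and no error rate or sample size is involved.

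This rests on two assumptions: that objectives are read through the inclusion criteria, and that reports state the population and data source as the criteria define them. It would deserve another look if the sponsor knew of a material number of COVID-19 patients with no EPIC record, or if BI were being used to enter such patients despite 5.312.

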5.4 Site Responsibilities

5.41 HMH abstract of data from the EPIC system.

5.42 All eligible patients with COVID-19 will be included.

5.5 Registry Data Collection

5.51 Research personnel approved by HMH will extract and organize data from the electronic health record into the database.

5.52 Data will be entered into the REDCap approved database only. All protected health information (PHI) will be handled to maintain HIPAA compliance. The REDCap system will store PHI but this information will not be exported for any analysis unless specifically approved by the IRB. In the REDCap forms, all PHI will be parked as “identifiers” and only deidentified datasets will not be exported and shared with anyone but the study team.

5.53 Key prognostic diagnostic fields, demographics, treatments, and outcomes will be populated with data. Structured and unstructured data in the patients’ electronic records will be reviewed to complete the population of the registry. The database however is not

intended to be an all-inclusive representation of the medical chart. Daily laboratories of routine nature will not be collected.

- 5.54 Adverse events may be scored and recorded using the common toxicity criteria (CTC). However, it will be the treating sites responsibility to report to the authorities/manufacturers any serious adverse events in accordance with standards of care for the institution and in compliance with local/national regulations.
- 5.55 This initiative is meant to be an observational database. No additional testing or treatment will be required for enrollment of a patient. All clinical care, including diagnostic and therapeutic decisions, will be at the sole discretion of the patient's treatment team.

5.6 Variables

Data points will be collected from the electronic medical record (or other HMH sources as available for patients with confirmed or suspected COVID-19. A partial listing is detailed below:

- 5.61 Key demographic variables include age, gender, race, zip code, past medical history documented co-morbidities, smoking history, etc.
- 5.62 Key diagnostic variables include date of diagnosis (COVID testing), blood count at time of hospitalization and/or entry to ICU care, chemistry panel, ferritin, ddimer, c-reactive protein, IL-6 levels, etc.
- 5.63 Key therapeutic variables include use of hydroxychloroquine, azithromycin, ventilator support, dialysis support, pressor support, etc.
- 5.64 Key outcome variables include will include need for hospitalization, duration of hospitalization, need for icu/ventilator support, duration of icu support, and death..

5.65 Key treatment center variables include hospital type (academic/ community), number of cases per hospital.

Data Analysis

5.71 COTA will provide basic descriptive analysis of the COVID-19 patients in a de-identified aggregated fashion. Survival and healthcare utilization analysis with time variables will utilize censoring and the Kaplan-Meier methodology. Multi-variable analysis for associations between demographic and/or treatment variables and key outcomes will be performed. Additional analysis will be performed per review of the data.

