3.1 Rationale for an Observational Database in COVID-19

Coronavirus disease 2019 (COVID-19) is a respiratory tract infection caused by SARS-CoV-2 virus, a novel betacoronavirus discovered in Wuhan, China in December 2019. Subsequently, the disease has spread globally and outbreaks have been identified in over 100 countries. In China, data extracted from medical records of 1099 hospitalized patients and outpatients with laboratory confirmed COVID-19, revealed a summary of clinical characteristics. The most common symptoms were fever (43% on admission and 88.7% during hospitalization), cough (67.8%) and diarrhea (3.8%). On admission, ground-glass opacity was the most common radiologist finding on CT scans (56.4%). According to another recent Chinese study evaluation of 72,314 cases, 80% of patients presented with mild disease and the overall case-fatality rate was about 2.3%. (1)

A more complete understanding of the epidemiology, presenting features, role of comorbidities in severity of illness, needs for and utilization of healthcare resources, effectiveness of therapeutic approaches including off-label use, and clinical outcomes is desperately needed. Well-designed clinical trials, although helpful in gaining regulatory approval of new agents, enroll only a fraction of available patients and may not always mirror “real world” scenarios. An outcome database may be able to provide rapid indicators of effective strategies. Collecting data from the electronic health records permits significantly detailed information to be analyzed while not interfering with the routine best medical care delivered by the treating physicians.

4 Registry Objectives

The principle objective of this Observation Outcomes Database is to build research-grade real world data that will serve as a platform to advance the scientific understanding and clinical care of patients with COVID-19 in order to provide best clinical treatment options.

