5.7 Quality Control

Unlike traditional data sources (ie, claims databases) the full medical record is analyzed by the abstractors allowing deep medical variables to be characterized. The principal investigators and COTA will perform statistical reviews to uncover “obvious” inaccuracies. However, the data will not undergo formal secondary reviews for accuracy. Investigators should understand the limitations of an observational database in drawing any conclusions.

6 Protection of Human Subjects

This document is a study protocol for an observational database study. This study is to be conducted according to United States and international standards of Good Clinical Practice (CFR Title 21 parts 11, 50, 54, 56, 312, International Conference on Harmonization and the Declaration of Helsinki), applicable government regulations and Institutional research policies and procedures.

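### Does listing organ support among therapies, with no stated time zero, mean drug comparisons will be adjusted for what happened after the drug?

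*Combined protocol and SAP*

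**What the plan says.** Section 5.6 describes the variables to be abstracted and says of its lists: "A partial listing is detailed below". Within it, 5.63 reads "Key therapeutic variables include use of hydroxychloroquine, azithromycin, ventilator support, dialysis support, pressor support, etc", and the outcomes in 5.64 include "need for icu/ventilator support, duration of icu support, and death". Ventilation is therefore in both lists; dialysis and pressors are only in the first.

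The analysis text is item 5.71. On time-to-event work it says "Survival and healthcare utilization analysis with time variables will utilize censoring and the Kaplan-Meier methodology". On modelling it says "Multi-variable analysis for associations between demographic and/or treatment variables and key outcomes will be performed". It gives no index date, covariate list or rule on when covariates are measured, and no other section does. Section 5.62 includes the date of diagnosis but does not call it a time origin.

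On purpose, objective 4.14 is to "Explore efficacy and toxicity of various treatment strategies", and section 4 presents the database as a platform to advance "clinical care of patients with COVID-19 in order to provide best clinical treatment options". Section 5.1 calls the database descriptive. The quality control section warns: "Investigators should understand the limitations of an observational database in drawing any conclusions".

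Item 1a of the synopsis (section 2) gives another list of data points. There oxygen support, dialysis and ECMO are separate entries, and the word treatment is attached to named drugs and anti-inflammatory agents.

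**The concern.** Ventilation that starts after a drug is a consequence of the course of disease and possibly of the drug. If it enters a model for the drug's effect on death as another treatment variable, two errors can follow. First, any benefit that works by preventing deterioration is conditioned away. Second, if the drug changes ventilation and unmeasured severity drives both ventilation and death, conditioning on ventilation makes treated and untreated patients unlike in severity and can produce an effect where there is none.

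Reading 5.63, 5.64 and 5.71 together, nothing stops an analyst from doing this, and no time zero separates baseline from later events. Treatment comparison is a stated aim, so the question is not idle. Unlike ordinary confounding by indication, the analyst introduces this error by adjusting, and a rule would prevent it. The general caution about observational data does not address timing.

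**Working it through.** **Step 1: what the text commits the analyst to.**

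| Point | What the protocol fixes | What it leaves open |
|---|---|---|
| 5.63 | Organ support and drugs are recorded under one heading | Their role in any model |
| 5.64 | Ventilator need is recorded as an outcome | Whether it may also be a covariate |
| 5.71, modelling | Associations of demographic and/or treatment variables with key outcomes | Which variables enter together, and the adjustment set |
| 5.71, Kaplan-Meier | Method and use of censoring | Time origin for each endpoint |
| Synopsis, item 1a | Dialysis, ECMO and oxygen support listed apart from drug treatment | Role in any model |

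The step from 5.63 to a wrongly adjusted model needs three further assumptions: that the treatment variables of 5.71 are the whole therapeutic list of 5.63, that they all enter one model, and that the support began after the drug. None is in the text. The wording in 5.71 leaves the choice of variables open, and synopsis item 1a points against the first assumption. The time-origin gap is also narrower than it looks: the durations of hospitalization and ICU support in 5.64 start at admission and ICU entry. What remains open is survival and the treatment comparisons.

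**Step 2: how large the error would be if it were made.** The protocol states no rates, sample size or effect, so there is no figure of its own to reproduce. Every input below is assumed. Both cases take drug use as unrelated to severity, and all ventilation as starting after the drug.

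*Effect removed.* Ventilation is 30% in controls and 30%, 26% or 22% with the drug. Mortality is 50% if ventilated and 8% if not, and the drug acts only through ventilation.

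- Control mortality: 0.30 × 0.50 + 0.70 × 0.08 = 0.2060.
- At 26%: 0.26 × 0.50 + 0.74 × 0.08 = 0.1892. Odds ratio (0.1892/0.8108)/(0.2060/0.7940) = 0.899; risk difference −0.0168.
- At 22%: 0.22 × 0.50 + 0.78 × 0.08 = 0.1724. Odds ratio (0.1724/0.8276)/(0.2060/0.7940) = 0.803; risk difference −0.0336.
- Mortality within each ventilator stratum is the same in both groups, so the adjusted odds ratio is 1.00 by construction.

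With an added direct odds ratio of 0.90 inside each stratum, treated mortality is 0.1929, 0.1769 or 0.1608. The total risk difference is then −0.0131, −0.0291 or −0.0452. Standardised to the pooled ventilator mix, it is −0.0131, −0.0127 or −0.0123.

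*Spurious effect.* Thirty per cent of patients are severe. Untreated ventilation is 15% (non-severe) and 65% (severe), so 0.70 × 0.15 + 0.30 × 0.65 = 0.30 overall. Death is 8% or 50% by severity alone, so the true odds ratio is 1.00. The last column comes from a logistic model with drug and ventilation, equal groups.

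| Treated ventilation, non-severe / severe | Overall | Adjusted odds ratio |
|---|---|---|
| 15% / 65% | 30% | 1.000 |
| 12.5% / 57.5% | 26% | 1.055 |
| 10% / 50% | 22% | 1.113 |
| 17.5% / 72.5% | 34% | 0.946 |
| 20% / 80% | 38% | 0.892 |

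Over 24 combinations of severity share, ventilation rates and death rates, the adjusted odds ratio is 1.000 throughout when the drug has no effect on ventilation, 1.036 to 1.075 with half the assumed effect, and 1.073 to 1.159 with all of it.

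**Step 3: what the figures show.** They confirm a known mechanism. They do not estimate a risk in this registry: rates, treatment assignment and the order of drug and ventilation are all supplied from outside it. For a patient already ventilated when the drug starts, ventilation is a legitimate baseline covariate, and omitting it would itself be an error. The figures say nothing about how a missing time origin would affect the Kaplan-Meier curves.

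**The case for a change.** The best argument for changing the plan is that treatment efficacy is listed as a primary objective, several groups may analyse the data (the analytic company and the network's own investigators), and one general sentence in 5.71 would give them a common timing rule. Section 5.62 adds to the looseness, because blood counts may come from hospital admission or from ICU entry, and the latter may follow drug start.

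Much of this stands. The silence is real, the mechanism is real, and a sentence would cost little. It does not stand that the plan, taken at its word, puts later organ support into drug-effect models. Nor would a generic sentence settle the matter. Section 5.71 enumerates no individual comparisons, so the time zero for each would still have to be chosen when the question is posed, and the sentence would only restate ordinary practice. Under the synopsis, analyses are run as research teams request them, or by network investigators after further human-subject review; that is where origin and covariates are naturally fixed. The variable lists are avowedly partial, so the absence of start dates from them does not show that the dates are not collected.

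**Conclusion.** The concern does not call for a change. Recording ventilation as both a therapy and an outcome is sound data collection, and the two lists do not contradict each other. What is missing is a standard analysis convention: name the time origin, adjust for what was known by then, and treat later organ support as an outcome or in a declared time-dependent or mediation analysis. A competent analyst supplies this for each question in an exploratory registry.

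If the convention were ignored, the harm would range from nothing to the complete loss of an effect that works through ventilation, or, in the main spurious-effect example, an odds ratio of about 0.89 to 1.11 where the truth is 1.00. That range rests wholly on assumed rates, on drug use unrelated to severity, and on ventilation always following the drug. The conclusion rests on 5.71 leaving the model open. It would be different if the plan had specified a drug comparison adjusted for organ support without regard to timing.
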